## **B. Efficacy Endpoint Analyses**

ORR and DCR will be summarized for all dose levels. The two-sided 95% confidence interval (CI) using the Clopper-Pearson method will only be provided at RP2D and overall.

PFS, and DoR will be summarized using the Kaplan-Meier (KM) method at by treatment group and overall. Estimates of median and PFS at 6 and 12 months, with the corresponding 95% CI will be reported for RP2D and overall. Swim lane plot for all time to event analysis by dose level and by wnt ligand dependency (DOR, PFS and duration of treatment).

Time to response, defined as (date of first documented response of CR or PR for patients who have a confirmed CR or PR – date of first treatment + 1) / 7, will be summarized descriptively among patients who reported a response.

Percent change from baseline in the sum of diameters of TLs will be summarized descriptively. Percent change from baseline in the sum of diameters of TLs for individual patient will be present in the spider plots – separate plots will be done by dose level and by Wnt ligand dependency. The best percent change in tumor size while on treatment will be presented in two waterfall plots. In one plot the bars will be color coded by dose level and in a separate plot by Wnt ligand dependency.

ORR and percent change in the sum of TL diameters will only be evaluated among patients with measurable disease (i.e., with target lesion identified) at baseline. All efficacy data as collected on the eCRF along with the derived parameters will be presented in data listings.

Given the small sample size in module 3, Duration of Response (DoR) and Time to Response will not be summarized for module 3 patients.

## **IX. Safety Analyses**

Safety analyses will be based on the Safety Population.

### **A. Exposure**

Exposure to RXC004 and Nivolumab will be summarized by dose cohorts and overall, for each module separately. All exposure parameters as well as all exposure data collected on the eCRF will be present in data listings.

The following exposure parameters of RXC004 will be summarized from the

- Total duration of exposure (weeks): calculated as (last RXC004 dosing date – first RXC004 dosing date + 1) / 7
- Total number of doses received: defined as number of doses received as collected on the RXC004 dose administration eCRF page from the first RXC004 dosing date to the last RXC004 dosing date.
- Any dose modifications: patients who have at least 1 RXC004 dose change (including dose reduction, missed dose or dose permanently withdrawn) along with the reason for dose modification will be summarized using frequency counts and percentages.
- Any dose reductions: patients with any dose reductions will be summarized using frequency counts and percentages by the following categories: any dose reductions, 1 dose reduction, 2 dose reductions.

The following exposure parameters of RXC004 will be summarized based on continuous dosing period (i.e., start from Cycle 1 Day 1). Cycle 0 dosing is excluded:

- Total duration of exposure (weeks) on continuous dosing: calculated as (last RXC004 dosing date – first RXC004 dosing date of C1D1 + 1) / 7
- Number of cycles for RXC004 on continuous dosing excluding Cycle 0: will be determined based on the last nominal visit as collected on CRF
- Number of completed cycles: a cycle will be considered complete if they have 14 days of therapy within a 3-week period from C1D1. The total number of completed cycles will be calculated as the total number of days the dose was received divided by 14 (Module 3 only).
- Cumulative actual dose received (mg): defined as total amount of actual dose (mg) received as collected on the RXC004 dose administration eCRF page from the first RXC004 dosing date to the last RXC004 dosing date.
- Cumulative planned dose (mg): defined as total amount of planned dose (mg) as recorded on the RXC004 dose administration eCRF page from the first RXC004 dosing date to the last RXC004 dosing date.
- Actual dose intensity (mg/week): defined as cumulative actual dose (mg) divided by total duration of exposure (weeks)
- Planned dose intensity (mg/week): defined as cumulative planned dose (mg) divided by total duration of exposure (weeks). If a patient had a reduced dose per investigator's assessment, then reduced dose will be considered as planned dose for the calculation of RDI.
- Relative dose intensity (%): calculated as (actual dose intensity / planned dose intensity) \* 100%.
- Relative dose intensity category: the calculated % relative dose intensity above will be summarized by the following categories using frequency counts and percentages: <60%; 60% ≤ and < 75%; 75% ≤ and < 90%; 90% ≤ and ≤ 100%; > 100%.

The number of capsules dispensed, returned and taken at each visit as collected on the RXC004 drug accountability eCRF page will be presented in data listings.

Duration of the RXC004, will be summarized as continuous variables.

For patients in Module 2, the following exposure parameters of Nivolumab will also be summarized:

- Total number of doses received: defined as number of doses received as collected on the Nivolumab dose administration eCRF page from the first Nivolumab dosing date to the last Nivolumab dosing date.
- Any cycle delay: patients who have any cycle delay, 1 cycle delay, 2 cycle delays,  $\geq 3$  cycle delays will be summarized using frequency counts and percentages.
- Any infusion interruption: patients who have any infusion interruption along with the reason will be summarized using frequency counts and percentages.

Number of Nivolumab doses will be summarized as continuous variables.

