## **5.3 Module 2 – RXC004 and Nivolumab Combination**

Based on the safety profile observed to date, a decision has been made by Redx and the SRC to start Module 2.

The reason for conducting this study module is to provide the first cancer patient safety and tolerability data with RXC004 in combination with nivolumab.

Module 2 will commence by enrolling patients with advanced solid tumours into a SAD/MAD monotherapy dose escalation arm. Eligible participants will be enrolled in dose-escalation cohorts treated with RXC004 given as an oral capsule dose in combination with a PD1 infusion. The dose of nivolumab will be a fixed dose of (480 mg every 4 weeks, and will remain at this dose level throughout the study. The dose of RXC004 will be escalated. The RXC004 starting dose for combination with nivolumab will be a lower dose than the highest confirmed safe and tolerated dose from the monotherapy study (Module 1). The RXC004 dose will be dose-escalated to the MTD in combination in as few dose-cohorts as possible. The RXC004 dose

used in Module 2 will not be escalated to exceed the MTD for RXC004 in monotherapy (2mg RXC004 QD).

Patients will take a single dose of RXC004 to evaluate single dose PK, then start on continuous RXC004 dosing up 3-7 days later in combination with nivolumab every 28 days (Cycle 1).

Each cycle will be 28 days from Cycle 1, Day 1.

Dose increments will be guided by safety data observed during Cycle 1, as well as on-going assessment of safety beyond Cycle 1 in earlier cohorts, plus PK and pharmacodynamic data as available. Every new dose cohort will be evaluated for the occurrence of a DLT during Cycle 0 or Cycle 1 of treatment. (Figure 5)

[figure not shown]
Patients will have the option to have their tumour tissue (primarily from an archival source) tested for genetic aberrations (including upstream Wnt pathway aberrations such as RNF43 mutations and RSPO-fusion) by next generation sequencing (NGS) or MassArray technologies.

RXC004 will be administered orally in combination with anti PD1 infusion in patients with advanced solid malignancies. There will be escalation of the RXC004 dose in each cohort with intensive safety monitoring to ensure the safety of the patients. The design of this Module 2 also allows the RXC004 & anti-PD1 combination tolerability and PK to be characterised in an unselected population of patients.

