### 5.3.7 Dose Modifications

RXC004 dose reduction and interruption are permitted. Nivolumab dose reduction is not permitted but dose interruption/delay is permitted.

RXC004 may be dose interrupted (withheld) for up to 14 days until a clinically significant (any grade) and/or a grade  $\geq 3$  related adverse event resolves to baseline or  $\leq$  grade 1. Patients that experience a RXC004 related adverse events that do not resolve to baseline or  $\leq$  grade 1 after 14 days of dose interruption/delay despite appropriate treatment must be discussed with Sponsor, before re-starting RXC004.

Adverse events that are assessed as being causally related nivolumab should be managed as per the Nivolumab Toxicity Management and Dose Modification Guidelines (Appendix 8). If either agent alone is interrupted or discontinued for a related-AE the other agent (nivolumab or RXC004) may be continued if the patient is judged (by the investigator) to be receiving clinical benefit. If a patient continues in the study on nivolumab alone, this treatment may be continued for a maximum of 12 months in total.

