Event	Action
Any event that meets nivolumab treatment hold (see Appendix 8)	Interrupt nivolumab and manage as per Appendix 8. Nivolumab can be re-started when event is resolved to $\leq$ Grade 1 and any steroid taper completed (to 10mg prednisone equivalent). RXC004 can continue whilst nivolumab is held, if the patient is judged (by the investigator) to be receiving clinical benefit.
Grade 3-4 toxicity (1 st event)	RXC004 related;  Interrupt RXC004 and provide supportive care, resume at the next lowest dose level when resolved (grade $\leq$ 2 or returns to baseline). Interruptions >14 days should be discussed with Sponsor before re-starting.  Nivolumab related;  See guidelines in Appendix 8
Grade 3-4 toxicity (subsequent recurrence of a previously experienced event)	RXC004 and/or nivolumab related; Permanently discontinue study treatment
All Grade events	Study treatment can be discontinued for any clinically significant AEs that in the investigator's opinion warrants treatment discontinuation.

Event	Action
Bone events	
Confirmed RXC004 related fragility bone fracture (excluding grade 1 vertebral deformities)	Permanently discontinue RXC004. Nivolumab can continue, if clinical benefit is judged by investigator for a maximum of 12 months total treatment.
Patients with a DXA scan showing $\geq 7\%$ worsening in BMD at lumbar spine or total hip compared to baseline	Permanently discontinue RXC004. Nivolumab can continue, if clinical benefit is judged by investigator for a maximum of 12 months total treatment.
An individual increase in $\beta$ -CTX of $\geq 350$ pg/ml from the baseline (screening) value or in individual measurement of $\geq 1000$ pg/ml	Permanently discontinue study treatment unless the patient has received clinical benefit (investigator assessment) and continued treatment is warranted.
COVID-19 infection	
Positive COVID-19 test	Interrupt RXC004, until acute symptoms have resolved. Interruptions $>14$ days should be discussed with Sponsor before re-starting.
Surgery	Interrupt RXC004 (max. 14 days b ), resume at full dose. RXC004 should be stopped 3 days prior to surgery and resumed approx. 10 days later. If the wound has not healed a further 7 days are permitted prior to re-starting RXC004 at the discretion of the Investigator and with approval of Sponsor Physician.  No stoppage is required for biopsy procedures.

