## **D. Nominal Timepoints**

Except response rate and data presented on continuous timescale, all by-visit summaries and analyses will be performed on nominal visits (i.e., actual visit as specified on the eCRF).

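### The SAP's visit-based count of RXC004 cycles can overstate RXC004 cycles for Module 2 patients who stop RXC004 and continue on nivolumab alone

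*SAP*

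**What the plan says.** **The counting rule.** SAP Section IX.A (Exposure), in the list of RXC004 parameters for the continuous dosing period, states: "Number of cycles for RXC004 on continuous dosing excluding Cycle 0: will be determined based on the last nominal visit as collected on CRF". It is not limited to any module. SAP Section VI.D explains what a nominal visit is: "all by-visit summaries and analyses will be performed on nominal visits (i.e., actual visit as specified on the eCRF". That is a visit label, not a dosing record.

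**The neighbouring rows.** These are tied to RXC004 dosing. The duration row reads "Total duration of exposure (weeks) on continuous dosing: calculated as (last RXC004 dosing date", minus the C1D1 dosing date, plus 1, divided by 7. The dose-count row uses the "number of doses received as collected on the RXC004 dose administration eCRF page from the first RXC004 dosing date" to the last one. The only cycle count based on days dosed, the number of completed cycles, is marked as Module 3 only.

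**Module 2 treatment.** Protocol Section 5.3 gives both drugs one cycle numbering: "Each cycle will be 28 days from Cycle 1, Day 1". Section 5.3.7 adds: "If either agent alone is interrupted or discontinued for a related-AE the other agent (nivolumab or RXC004) may be continued", if the investigator judges that there is clinical benefit. It also says: "If a patient continues in the study on nivolumab alone, this treatment may be continued for a maximum of 12 months in total". Table 6 applies this to fragility fracture and to loss of bone mineral density: "Permanently discontinue RXC004. Nivolumab can continue, if clinical benefit is judged by investigator for a maximum of 12 months total treatment". It has a similar entry for dysgeusia with more than 20% weight loss. Appendix 2 places nivolumab dosing at the Cycle X Day 1 visits, and its footnote k repeats the 12-month limit.

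**The concern.** Once RXC004 is stopped and nivolumab goes on, the patient keeps attending visits that carry cycle numbers. A rule that reads the RXC004 cycle count off the last such visit turns nivolumab-only cycles into RXC004 cycles. The error can only go upwards, and it falls on patients who stopped RXC004 while nivolumab continued, often because of an RXC004-related event.

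At stake is the accuracy of one descriptive row in the Module 2 exposure table and its agreement with the row above it. Module 2 is planned at approximately 18 patients in small dose cohorts, so one affected patient can move a cohort's mean, SD and maximum visibly.

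**Working it through.** The plan states no cycle count, so there is no figure of its own to reproduce. The check sets the SAP rule against a count from dosing dates for hypothetical Module 2 patients.

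**Inputs from the documents**
- Cycle length: 28 days from C1D1 (Protocol 5.3).
- Limit on nivolumab when continued alone: 12 months in total (Protocol 5.3.7).
- RXC004 duration in weeks: (last RXC004 dosing date − C1D1 dosing date + 1)/7 (SAP IX.A).

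**Assumptions**
- RXC004 was taken from C1D1 to day 28, 56 or 84 and then stopped permanently, with no whole cycle missed before that.
- Nivolumab visits ran without delay, and the last numbered visit was C3, C6 or C13.

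**Last possible cycle.** Day 1 of cycle k falls on day 1 + 28(k − 1). C13D1 is day 1 + 28 × 12 = 337, and C14D1 is day 1 + 28 × 13 = 365. Also 365/28 = 13.04. Twelve months therefore holds about 13 cycles. If the day-365 visit were attended and labelled C14, each C13 row below would rise by one.

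**Formulas**
- Cycles by dosing dates: last RXC004 day/28, rounded up.
- Cycles under the SAP rule: cycle number of the last nominal visit.
- Excess: the second minus the first.

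| Last RXC004 day | Duration row (weeks) | Cycles by dosing | Last nominal visit | Cycles under SAP rule | Excess |
|---|---|---|---|---|---|
| 28 | 28/7 = 4.0 | 1 | C3 | 3 | 2 |
| 28 | 4.0 | 1 | C6 | 6 | 5 |
| 28 | 4.0 | 1 | C13 | 13 | 12 |
| 56 | 56/7 = 8.0 | 2 | C3 | 3 | 1 |
| 56 | 8.0 | 2 | C6 | 6 | 4 |
| 56 | 8.0 | 2 | C13 | 13 | 11 |
| 84 | 84/7 = 12.0 | 3 | C6 | 6 | 3 |
| 84 | 12.0 | 3 | C13 | 13 | 10 |

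If RXC004 stops within the last cycle attended, the two counts agree.

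**Conflict between rows.** For the patient with a last RXC004 dose on day 56 and a last visit at C13, the table would show 8.0 weeks of RXC004 beside 13 RXC004 cycles. Thirteen cycles correspond to 13 × 4 = 52 weeks.

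**Upper-bound effect on a cohort.** Take six patients, five with 2 cycles each (assumed) and one who stopped on day 28 and stayed on nivolumab to C13.
- Mean by dosing: (1 + 5 × 2)/6 = 1.83.
- Mean under the SAP rule: (13 + 5 × 2)/6 = 3.83.
- Median: 2 either way. Maximum: 2 against 13.

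**The case against.** **The wording may be meant more narrowly.** The list's lead-in restricts it to RXC004 on continuous dosing, and a nivolumab-only visit is not that. A fully literal reading also fails, because the Module 2 schedule goes on to discontinuation, 30-day, 90-day and PFS follow-up visits that have no cycle number. A programmer must supply some restriction, and the last visit on the RXC004 dosing page is a natural choice. That reading is possible and would remove the problem. It is not stated, however, and neighbouring bullets name the dosing page when they mean it. Another programmer could equally take the last numbered cycle visit.

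**Large discrepancies may be rare.** Thirteen against 1 needs a patient who stops RXC004 in Cycle 1 and then has a full 12 months of nivolumab. Table 6 stops both agents for Grade 3 or 4 colitis on the combination and for recurrent Grade 3–4 toxicity. Protocol Section 1.7.1 reports no significant BMD loss on RXC004 and no spontaneous fractures since prophylactic denosumab was introduced. The median is also reported, and it does not move in the cohort above. All of this stands, and it is why 13 against 1 is given only as an upper bound. It does not close the broader route in Section 5.3.7, which covers discontinuation for any related adverse event.

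**Effect on tolerability conclusions.** A reader might infer that the count distorts the main tolerability evidence or the choice of dose. The documents do not support that. No section gives the cycle count such a role. Escalation rests on DLTs and review by the Safety Review Committee, and tolerability is also shown through RXC004 duration, doses, modifications, dose intensity and adverse events leading to withdrawal, reduction or interruption. The patient listings would also expose a mismatch.

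**Modules 1 and 3.** A reader might extend the point to a patient who attends a Day 1 visit in these modules and is not dosed. That depends on how the eCRF labels such a visit, which the documents do not show. Module 3 also has its own count based on days dosed.

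**Conclusion.** The point holds for Module 2 and for one descriptive row. As written, the rule can report RXC004 cycles that were not given to patients who continued on nivolumab alone, and it can contradict the duration row beside it. The size is 1 to about 12 excess cycles per affected patient under the assumed stopping days and last visits. The effect on the Module 2 summary cannot be sized, because the number of nivolumab-only patients is not given.

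The conclusion assumes that the nominal visit means the numbered visit label on the eCRF, as SAP Section VI.D describes it, and not the last entry on the RXC004 dosing page. RXC004 duration, cumulative dose, dose intensity and the DLT-based decisions are unaffected. This is worth correcting because the stated rule can give a wrong number and the repair is simple; it does not threaten the study's conclusions.

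**What to change.** Replace the bullet in SAP Section IX.A with a rule such as: *the number of RXC004 cycles is the number of cycles, excluding Cycle 0, in which at least one RXC004 dose is recorded on the RXC004 dose administration eCRF page.* If that page was the intended source all along, the sentence simply makes it explicit.

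No further nivolumab parameter is needed: SAP Section IX.A already counts nivolumab doses from that drug's own administration page.

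The cost is one sentence and a small change to the exposure program, with no new data. The SAP Introduction allows changes until database lock. After lock, the same definition can be applied and recorded in the study report as a deviation from the plan.

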**Table 3. Intermittent Dose Schedule for Module 3**

Planned Dose	Planned Dose Schedule	Actual Dose	Actual Dose Schedule
2.0 mg QD	2 weeks on/1 week off	2.0 mg QD	2 weeks on/1 week off

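### SAP IX.A leaves the scheduled week off after the last on-block out of the mg/week denominator, so Module 3 dose intensity and exposure duration are misstated (minor)

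*SAP*

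**What the plan says.** SAP IX.A (Exposure) defines two RXC004 durations. The first runs from the first RXC004 dose to the last. The second belongs to a block introduced by "The following exposure parameters of RXC004 will be summarized based on continuous dosing period (i.e., start from Cycle 1 Day 1). Cycle 0 dosing is" (the sentence goes on to leave Cycle 0 out); it is labelled "Total duration of exposure (weeks) on continuous dosing: calculated as" and is "calculated as (last RXC004 dosing date – first RXC004 dosing date of C1D1 + 1) / 7". Both end on a dosing day.

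Dose intensity sits in the second block. Its numerator, the cumulative actual dose, is "defined as total amount of actual dose (mg) received as collected on the RXC004 dose administration eCRF page", from first to last dosing date. The ratio is "Actual dose intensity (mg/week): defined as cumulative actual dose (mg) divided by total duration of exposure (weeks", and the planned version has the same denominator: "Planned dose intensity (mg/week): defined as cumulative planned dose (mg) divided by total duration of exposure (weeks". Neither bullet repeats the words that mark the duration as the one for continuous dosing. Relative dose intensity (RDI) is actual over planned.

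The Module 3 schedule table in SAP IV.A lists one schedule, 2.0 mg QD, "2 weeks on/1 week off". Protocol 5.4.4 (Arm 2) makes that a 21-day cycle, so the week off is part of the cycle. The only exposure rule in IX.A specific to Module 3 is the number of completed cycles, obtained as days dosed divided by 14. Nothing extends duration to the end of a cycle.

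**The concern.** First-to-last-dose duration suits daily dosing, where the last dose is the end of treatment. On a schedule with planned breaks it treats identical breaks differently: a break followed by another dose is in the denominator, and the final break is not. A patient who takes every capsule should show the same mg/week after any number of full cycles. Under IX.A the figure depends on how many cycles were given, and it is highest for the shortest treatment.

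Protocol 5.4 says Module 3 looks at whether short treatment breaks can reduce toxicities such as dysgeusia. Mg/week is the line of the exposure table that shows how much drug the schedule delivers per unit of time. Exposure is summarised in the Safety Population, so one-cycle patients are included, and with 6 evaluable patients planned per arm a few of them can move the summary.

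**Working it through.** The documents give no dose-intensity value, so there is no figure to reproduce. The check applies the IX.A definitions to a fully compliant patient.

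**Inputs**
- Dose per cycle: 14 days × 2 mg = 28 mg (SAP IV.A Module 3 schedule table; protocol 5.4.4, Arm 2).
- Cycle length: 21 days (protocol 5.4.4).
- SAP duration: last dosing date − C1D1 + 1, divided by 7 (SAP IX.A).
- Cycle 0 in Module 3: 3 to 7 days (protocol 5.4.4), used only for the alternative reading.

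**Reading 1: duration from C1D1.** After n full cycles the last dose falls on day 21n − 7.
- SAP duration = (21n − 7)/7 = 3n − 1 weeks. With the final week off it is 3n weeks.
- SAP intensity = 28n/(3n − 1) mg/week. With the final week off it is 28n/(3n) = 9.33 mg/week.
- Excess = 3n/(3n − 1) − 1.

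| Full cycles | Dose (mg) | SAP weeks | SAP mg/week | With final week off | Excess |
|---|---|---|---|---|---|
| 1 | 28 | 2 | 14.0 | 9.33 | +50% |
| 2 | 56 | 5 | 11.2 | 9.33 | +20% |
| 3 | 84 | 8 | 10.5 | 9.33 | +12.5% |
| 4 | 112 | 11 | 10.18 | 9.33 | +9.1% |
| 6 | 168 | 17 | 9.88 | 9.33 | +5.9% |

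Continuous 2 mg daily is 2 × 7 = 14.0 mg/week, the one-cycle value.

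**Reading 2: duration from the Cycle 0 dose.** With g days between the Cycle 0 dose and C1D1, one cycle gives 28/((14 + g)/7).
- g = 3: 28/(17/7) = 11.53 mg/week, +23.5% against 9.33.
- g = 7: 28/(21/7) = 9.33 mg/week, 0%.

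The 0% is a coincidence: seven days of washout before C1D1 stand in for the seven missing days at the end.

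**RDI.** The denominator cancels. With 24 of 28 mg taken, (24/2)/(28/2) = (24/3)/(28/3) = 85.7%.

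**The 4 days on/3 days off arm, only if it is reported.** It is in protocol 5.4.4 but not in the SAP schedule table. One 21-day cycle is 12 × 2 = 24 mg over 18/7 weeks = 9.33 mg/week, against 24/3 = 8.0: +16.7%.

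**The case against.** The strongest case against acting is that little depends on this figure. RDI and its categories are correct. Cumulative dose, number of doses and completed cycles are reported, all exposure data are listed by patient, and the schedule is stated openly. There is no hypothesis test, and none of Module 3's stated aims uses mg/week. All of that stands, and it is why the point is minor.

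The size also depends on a reading. The intensity bullets use the label of the first duration, which includes Cycle 0. The block heading favours C1D1, but the text is ambiguous.

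No end-of-exposure rule is perfect. If off-days are added only when an on-block is finished, a patient stopping after 13 doses in cycle 1 still shows 26/(13/7) = 14.0 mg/week, and one more dose gives 28/3 = 9.33. That stands as a limitation and calls for a footnote.

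Four stronger readings are tempting, and the documents do not support them:
- *A typical patient is overstated by 20%.* One might reach this by equating Module 1's median exposure of about 7 weeks with two cycles. Seven weeks from C1D1 ends on day 49, which is C3D7, inside an on-block: 35 × 2 = 70 mg over 7 weeks = 10.0 mg/week, +7.1%. That median also comes from a different module and population.
- *RDI conceals an error.* RDI measures adherence to plan, and it does so correctly here.
- *Comparison with Module 1 is biased.* No such comparison is planned; modules are summarised separately.
- *Cycles are miscounted.* The number of cycles "will be determined based on the last nominal visit as collected on CRF", so a patient with 28 dosing days who attends C3D1 without dosing counts as 3. The next bullet, for Module 3 only, reports 28/14 = 2 completed cycles, which largely answers this.

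**Conclusion.** The point holds as a minor error in a descriptive rule. For 2 weeks on/1 week off, IX.A omits the scheduled off-week after the last completed on-block. It therefore overstates actual and planned mg/week and shortens total duration by one week. The excess for a fully compliant patient is 50% after one full cycle and at most 20% from two full cycles on.

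These sizes assume that duration is counted from C1D1, that cycles are complete, and that the 21-day cycle is the right reference period. Counting from Cycle 0, and keeping the numerator at 28 mg, the one-cycle excess is 0% to 23.5%; the final week off is still missing. RDI and its categories, cumulative dose and completed cycles are unaffected.

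**What to change.** In SAP IX.A:

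1. State that actual and planned dose intensity use the duration from C1D1.
2. For Module 3, when the patient reached the end of the last scheduled on-block, extend the end date by that block's scheduled off-days: 7 for 2 on/1 off, and 3 for 4 on/3 off if that arm is reported. Cap the end date at death or data cut-off. Use this end date for total duration and for both dose intensities.
3. Footnote the table: for patients who stop within an on-block, exposure ends at the last dose, so their mg/week reflects on-treatment days and can exceed the scheduled rate.

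The cost is a short addition to the SAP and a few lines of code, with no new data and no change to study conduct. The downside is that reported mg/week becomes lower and steps down at the end of an on-block.

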### **K. Data Display Characteristics**

Data displays produced for this study will include three types—summary tables, data listings, and figures. Unless stated otherwise, data listings will be produced for all recorded data. Summary tables will be produced as specified in the following sections. Additional data listings will be produced for outcome measures that involve extensive procedures to derive the analyzed outcomes. Figures will be produced when specified in sections to follow.

Data listings will simply list the data recorded on the eCRF or derived for each patient. They will be ordered by module, dose cohort, site, patient number, and date/time of assessment. When expedient, additional levels of ordering hierarchy may reflect subsets of assessments within patient. Data listings will not display patient initials.

Summary tables will display summary statistics calculated for each module and dose cohort, as well as overall within each module, unless described otherwise in following sections.

Unless stated otherwise in relevant sections to follow, continuous data will be summarized descriptively with the number of non-missing values, mean, standard deviation, minimum, median, and maximum. Categorical data will be summarized using frequency counts and percentages.

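### SAP IX.A gives two rules for completed Module 3 cycles that conflict once any cycle is not full; its RDI is relative to the prescribed dose and should be labelled so

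*SAP*

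**What the plan says.** **Completed cycles.** One bullet in SAP IX.A, for Module 3 only, holds two statements. The first is a definition: "a cycle will be considered complete if they have 14 days of therapy within a 3-week period from C1D1". The second is a calculation: "completed cycles will be calculated as the total number of days the dose was received divided by 14". SAP Table 3 of the design section gives the Module 3 schedule as "2 weeks on/1 week off". The bullet sits in a block described as "based on continuous dosing period (i.e., start from Cycle 1 Day 1). Cycle 0 dosing is excluded", so the single Cycle 0 dose does not enter the count.

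**RDI.** The SAP divides actual by planned dose intensity, each per week over the same duration. Cumulative planned dose is "defined as total amount of planned dose (mg) as recorded on the RXC004 dose administration eCRF page". If the investigator has reduced the dose, "then reduced dose will be considered as planned dose for the calculation of RDI". RDI is then tabulated in five bands (below 60%, 60 to below 75%, 75 to below 90%, 90 to 100%, above 100%).

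**The concern.** The completed-cycle bullet can be programmed in two ways, and the results differ exactly when adherence is imperfect, which is when the summary is of interest. Missed days are to be expected. Protocol Table 7 does not let a dose more than 4 hours late be taken, and the Module 3 evaluability rule (SAP VI.J) asks for only 80% of the intended dose over Cycles 1 and 2. With 6 evaluable patients planned per arm (SAP IV.C), one patient can visibly shift the summary.

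The RDI rule raises a question of meaning. Numerator and denominator fall together after a reduction, so the ratio shows how well the patient kept to the current prescription. A reader who takes it as dose delivered over dose assigned would misread it. Module 3 asks whether intermittent dosing could replace dose reduction, so that reading matters most there.

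**Working it through.** The plan gives no numerical result for either quantity, so there is no figure to reproduce. The dosing patterns below are illustrative assumptions; the rules and schedule are the SAP's.

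**1. Completed cycles.** Inputs: two weeks of daily dosing per 21-day cycle, so 14 scheduled dosing days. Let d_k be the dosing days in cycle k, at most 14.

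- Definition: the number of cycles with d_k = 14.
- Formula: (sum of d_k) / 14.
- Formula minus definition: (dosing days in incomplete cycles) / 14. This is never negative, and is zero only if no doses fall in an incomplete cycle.

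| Dosing days per cycle | Definition | Formula |
|---|---|---|
| 14, 14, 14, 14 | 4 | 56/14 = 4.0 |
| 14, 14, 14, 11 | 3 | 53/14 = 3.8 |
| 14, 14, 7, 7 | 2 | 42/14 = 3.0 |
| 14, 7 (partial last cycle) | 1 | 21/14 = 1.5 |
| 12, 12 | 0 | 24/14 = 1.71 |
| 13 in each of six | 0 | 78/14 = 5.57 |

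Rounding down reconciles the cases with one incomplete cycle (3.8 to 3, 1.5 to 1) but not the others: 14, 14, 7, 7 still gives 3 against 2, and six cycles of 13 days give 5 against 0. The 12, 12 patient took 24/28 = 86% of scheduled doses and so meets the 80% dose threshold, yet has no completed cycle by the definition.

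**2. RDI.** With actual dose A, planned dose P and weeks W, RDI = (A/W)/(P/W) = A/P. If P follows the reduced dose and no dose is missed, A = P and RDI = 100%, whatever the size or timing of the reduction.

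Take 7 weeks (49 days) of daily dosing, the approximate Module 1 median exposure given in SAP IV.A, with a reduction after day 21:

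- 2 to 1.5 mg: (21×2 + 28×1.5)/(49×2) = 84/98 = 85.7% of assigned dose.
- 2 to 1 mg: (21×2 + 28×1)/(49×2) = 70/98 = 71.4% of assigned dose.

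Both patients fall in the SAP's 90 to 100% band. Against the assigned dose they would fall in the 75 to below 90% and 60 to below 75% bands.

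Module 3, two cycles, 2 to 1.5 mg after Cycle 1: (14×2 + 14×1.5)/(28×2) = 49/56 = 87.5% of assigned dose; the SAP's RDI is again 100%.

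**The case against.** **The RDI rule is a disclosed definition.** This stands. Neither document defines RDI against the assigned dose, so the rule is not an error or an internal contradiction.

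**Reductions are reported elsewhere.** This also stands. A reader might infer that the plan hides dose reductions, but it does not. SAP IX.A counts patients with reductions and IX.B tabulates adverse events leading to them. Also, "Summary tables will display summary statistics calculated for each module and dose cohort", and for daily dosing in Modules 1 and 2 actual mg/week within a cohort is proportional to dose delivered over dose assigned (84/7 = 12 and 70/7 = 10, against 14). Module 3 mg/week is a poorer substitute because the duration stops at the last dose and omits a final off-week. The reduced two-cycle patient shows 49/5 = 9.8 mg/week, above the scheduled 28/3 = 9.33, while an unreduced patient of the same duration shows 56/5 = 11.2.

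**Strict counting can understate exposure.** A patient taking 13 of 14 doses in every cycle scores zero. This is fair, and is why dosing days should be shown beside the count.

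**The documents do not say which cycle rule was intended.** True. But the definition is the only statement of what makes a cycle complete, so a figure labelled completed cycles should follow it.

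**Held days.** A reader might infer that RDI cannot be reproduced when dosing is held and resumed lower. With 21 days at 2 mg, 14 held and 14 at 1.5 mg (63 mg given), RDI is 63/91 = 69.2%, 63/84 = 75.0% or 63/63 = 100% if held days carry 2, 1.5 or 0 mg as planned dose. But planned dose comes from an eCRF page that is not in the documents. The spread shows missing detail, not a demonstrated defect.

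**Conclusion.** The completed-cycle bullet is wrong as written: its formula does not compute its own definition. It exceeds the definition by the dosing days in incomplete cycles divided by 14, for example 3.0 against 2 or 5.57 against 0. This rests on 14 scheduled days per cycle and on missed doses or a partial last cycle; with full cycles the two agree.

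The RDI point is an improvement in labelling and completeness. The arithmetic is certain, but the convention is open and the reductions are visible in other tables.

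Two stronger readings are not supported. One is that either issue could distort dose selection. Escalation in Modules 1 and 2 rests on dose-limiting toxicities, the Safety Review Committee takes interruptions and reductions into account directly (Protocol 3.2), and no decision rule uses RDI or completed cycles. Neither is among the SAP III.B safety endpoints or the Protocol 9.2.2 measures. The other is that the protocol's 4-days-on/3-days-off arm, with 12 dosing days per cycle, could never register a completed cycle. SAP Table 3 lists only the two-weeks-on/one-week-off schedule, so the 14-day rule fits the arm the SAP covers.

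Priority is low.

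**What to change.** **Completed cycles (Module 3).** Delete the division by 14 as the definition of the count. Count cycles one by one against the stated definition, taking the recorded Day 1 of each cycle as its start. Because one missed day makes a cycle incomplete, report total dosing days beside the count, or dosing days divided by 14 labelled *cycle equivalents*.

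**RDI.** Label the current ratio as relative to the prescribed dose. For Modules 2 and 3, add a ratio of dose given to cohort-assigned dose times the dosing days scheduled from C1D1 to the last dosing date. Held days count as scheduled. In Module 3, take scheduled days from a fixed 21-day calendar that a hold does not shift; this is an analysis convention and does not govern when dosing resumes. Check: a fully compliant 2 mg Module 3 patient whose last dose is Cycle 3 Day 3 scores 62/(2×(14+14+3)) = 62/62 = 100%. Module 1, whose database is already locked (SAP I), needs no new table.

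**Clarifications only.** State what planned dose held days carry. State that the C1D1-based duration is the divisor for mg/week, as the block's description already implies. Footnote that Module 3 mg/week can omit a final off-week.

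**Cost.** SAP wording and a little programming on data already collected. The added ratio will be lower than the current one for patients with reductions. It still ends at the last dose, so a hold that ends in discontinuation is seen only in the discontinuation tables.
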